This study is a phase IIb trial using optimal dose of TOOKAD® Soluble and optimal light-energy level conditions that were determined in previous phase I and II studies and confirmed by the phase III studies among patients with localized prostate cancer. Partial gland ablation therapy using thermal approaches, as an alternative to radical treatments for low-volume prostate cancer, is a treatment option currently being offered to men with prostate cancer in the U.S. as a tailored means to manage their disease with fewer side effects. Previous studies of TOOKAD® Soluble treatment have suggested that this non-thermal approach is an effective therapeutic strategy to achieve ablation of the prostatic tissue that contains the cancer lesion in this patient population. Considering the available clinical data, a phase IIb is considered appropriate at this stage, with the main aim of confirming, in intermediate risk patients, previous findings in low and favorable intermediate risk prostate cancer patients. Moreover, a single center design was also considered appropriate, as it allows for optimal standardization of the technique and better control over data acquisition.

NUMBER OF PATIENTS:

In order to obtain at least 44 evaluable patients, a total of 50 patients will be included and will be treated with TOOKAD® Soluble VTP in this study.

DRUG DESCRIPTION AND PREPARATION:

TOOKAD® Soluble - padeliporfin di-potassium (WST11) Drug Product is a dark coloured powder for solution for injection. It is packaged in amber glass vials. It is manufactured in two different presentations:

- 200 mg TOOKAD® Soluble in a 30 mL vial with blue flip-off cap, to be reconstituted, just before administration, with 20 mL of 5% dextrose solution for injection
- 400 mg TOOKAD® Soluble in a 50 mL vial with white flip-off cap, to be reconstituted, just before administration, with 40 mL of 5% dextrose solution for injection

The two presentations have the same formulation which is produced in exactly the same process and they differ only in the amount of TOOKAD® Soluble per vial, the size of the vial and the colour of the flip-off cap.

For both presentations the final concentration of TOOKAD® Soluble solution to be injected is 10 mg/mL.

INCLUSION CRITERIA:

Subjects will be eligible for inclusion in the study if all of the following criteria are met:

1. Men over 18 years of age.

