- Patients' reported outcome measures (PROMs) impairment: urinary symptoms using IPSS and erectile functions using IIEF prior to treatment beginning and then 1, 3, 6, 12, 24, 36, 48 and 60 months after completing treatment
- Severe prostate cancer-related events: cancer extension to T3, metastasis or prostate cancer-related death
- Use of secondary prostate cancer treatment following VTP will include surgical removal of the prostate gland, radiation treatment to the prostate gland, use of hormone or chemotherapies.
- Adverse events
- Serum PSA measurements in ng/mL.

SAMPLE SIZE JUSTIFICATION

A proportion of responders of $r=70\%$ at 12 months is considered to be a clinically significant expectation in localized intermediate-risk prostate cancer patients.

Based on historical data in similar series of patients, a minimum of $N=44$ patients is required to test the null hypothesis $H_0: "r \leq 70\%"$ vs. $H_1: "r > 70\%"$, with 80% power and 5% as alpha risk.

MANUFACTURING INVESTIGATIONAL PRODUCT:

TOOKAD® Soluble is manufactured by Praxis Pharmaceutical S.A, Vitoria-Gasteiz, Spain.

TOOKAD® Soluble batches are released by Steba Laboratories, Ness Zion, Israel.

Laser equipment: Intermedic Arfran S.A, Spain

FLOW CHART: Schedule of Events

Procedure	V1 and screening period	V2 VTP	V3 Day 7+/- 2 days	V4 Month 1 +/- 1 wk	V5 Month 3 +/- 2 wks	V6 Month 6 +/- 2 mos	V7 Month 12 +/- 2 mos	V8-11 Annual f/u +/- 3 mos
Informed Consent	X							
Inclusion/exclusion Criteria	X							
Medical History	X							
TNM Staging	X							
VTP Treatment		X						
Clinical Examination	X	X ^a						
Prostate Biopsy	X ^b ≤6mos before consent				X ^c		X	X ^d
Digital Rectal Examination	X							
Prostate Specific Antigen	X ^e	X		X	X	X	X	X
Standard Hematologic Tests	X ^e	X ^a		X	X	X	X	X
Standard Blood Chemistry Tests	X ^e	X ^a		X	X	X	X	X
Standard Blood Coagulation Tests	X ^e							
Additional Inclusion Blood Tests	X ^e							
Prostate Volume	X	X						
MRI	X ^d				X		X	X ^d
Patient-Reported Outcome Measures (PROMs)	X			X	X	X	X	X
Study Medication		X						
Concomitant Medications	X	X ^a	X	X	X	X	X	X
Adverse Events		X ^a	X	X	X	X	X	X

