3.3 Secondary objectives

1. To describe the rate of responders, with response defined as the absence of any Gleason grade 4 or 5 biopsy on or before months 24, 36, 48 and 60. If a subject is retreated following a positive biopsy at 3 months and subsequent biopsy shows absence of gleason grade 4 or 5, the subject will be considered to have responded;
2. To describe the rate of responders, with response defined as the absence of any prostate cancer on biopsy on or before months 3, 12, 24, 36, 48 and 60. If a subject is retreated following a positive biopsy at 3 months and subsequent biopsy shows absence of any cancer, the subject will be considered to have responded;;
3. To describe the rate of responders, with response defined as the absence of any Gleason grade 4 or 5 biopsy on or before months 12, 24, 36, 48 and 60 in the treated lobe. If a subject is retreated following a positive biopsy at 3 months and subsequent biopsy shows absence of gleason grade 4 or 5, the subject will be considered to have responded;
4. To describe the rate of responders, with response defined as the absence of any prostate cancer on biopsy on or before months 3, 12, 24, 36, 48 and 60 in the treated lobe. If a subject is retreated following a positive biopsy at 3 months and subsequent biopsy shows absence of any cancer, the subject will be considered to have responded;
5. To describe the change in biopsy results between 3, 12, 24, 36, 48 and 60 months after TOOKAD® Soluble-VTP.
6. To describe changes in urinary and erectile function and their potential impact on QOL using International Prostate Symptom Score (IPSS) and International Index of Erectile Function (IIEF) questionnaires up to 60 months;
7. To describe the occurrence of adverse events of TOOKAD® Soluble VTP treatment in patients with localized prostate cancer;
8. To describe the occurrence of severe prostate cancer-related events: cancer extension to T3, metastasis and prostate cancer-related death.

9. To document the occurrence of secondary prostate cancer therapies following VTP treatment.
10. To describe changes in PSA from blood samples following TOOKAD® Soluble-VTP.

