10.2.2.5 Drop-outs and censored patients

All subjects who withdraw from the trial before the VTP procedure will be considered as drop-outs. Every effort will be made to minimize dropouts.

Eligible subjects who undergo additional radical therapy (surgery or radiation) after the VTP procedure or receive medical therapies (hormone or chemotherapies) will be kept in the intention to treat population but will be excluded from the per protocol population.

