Quality of life is assessed using validated questionnaires. The IPSS comprises seven questions on the urinary symptoms plus one general question about the QOL related to urinary symptoms, whereas the IIEF comprises 15 questions. For both questionnaires, patients self-rate their responses: for the IPSS, using a six-point scale where 0 indicates 'none' or 'normal', whereas 5 indicates the worst response; for the IIEF, using a five- or six-point scale where 0 indicates 'no sexual activity', and 5 indicates the best response (questions 1 to 10), or where 1 indicates the worst response and 5 the best response (questions 11 to 15).

- Rate of adverse events following treatment

As described in section 9.1, adverse events will be recorded and reported descriptively. Events will be annotated and graded according to National Cancer Institute Common Toxicity Criteria version 4.03.

- Severe prostate cancer-related events: cancer extension to T3, metastasis or prostate cancer-related death

Stage progression to T3 disease (extracapsular extension or seminal vesical invasion), metastasis or cancer-related death will be assessed based on tissue confirmation with biopsy or post-mortem evaluation. Radiographic evidence of suspicious findings will not be utilized unless confirmed with tissue sampling.

- Use of secondary cancer therapies following VTP treatment

Patients who proceed to additional therapies for prostate cancer treatment such as radiation, surgery, hormone or chemo therapies will be documented. Adjunctive surgical or medical therapies that are not intended as cancer treatments but for management of post-treatment related events will be recorded under adverse event reporting and graded appropriately.

- Serum PSA measurements in ng/mL.

Patients blood will be drawn and PSA level determined at 1, 3, 6, 12 months and annually thereafter. Changes from baseline will be determined.

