### **Secondary efficacy analysis**

#### **Biopsy results**

Biopsy results at each follow-up (3, 12, 24, 36, 48 and 60) for each definition of positive biopsy will be given as cumulative frequency, along with 95% C.I., with radical therapy as a competing risk. The alternative definitions of positive biopsy are:

1. Presence of any pattern 4 or 5 disease (primary endpoint)
2. Presence of cancer of any grade
3. Presence of any pattern 4 or 5 disease in the treated lobe
4. Presence of cancer of any grade in the treated lobe

Analyses will be repeated with radical treatment counted as an event. As retreatment at 3 months is allowed, 3 month results will be treated as a binary endpoint with 95% C.I. presented in a table.

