#### **Initiation of additional therapy**

Additional prostate cancer treatment is defined as any treatment for prostate cancer other than TOOKAD® Soluble-VTP, including surgery, radiotherapy (external beam, brachytherapy, focused), high intensity focused ultrasound, cryotherapy, hormonal therapy for cancer, chemotherapy for cancer.

The time to initiation of therapy will be analyzed using Kaplan-Meier estimates, presented as a survival curve with corresponding 95% confidence intervals. Subjects who did not initiate any therapy will be censored at the time of study termination. The corresponding Kaplan-Meier curve will also be presented. As a sensitivity analysis, this analysis will be repeated excluding ablative therapies and hormonal therapy, that is, an analysis of time to radical therapy (surgery, radiotherapy). Tables and figures will be provided as appropriate.

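### The SAP's biopsy analyses allow only for radical therapy, although the SAP's own definition of additional treatment also covers focused ultrasound and cryotherapy

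*Protocol*

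**What the plan says.** - **SAP, Initiation of additional therapy.** Additional treatment is any treatment for the cancer apart from study VTP, "including surgery, radiotherapy (external beam, brachytherapy, focused), high intensity focused ultrasound, cryotherapy, hormonal therapy for cancer, chemotherapy for cancer". A sensitivity analysis then removes ablative and hormonal therapies and calls what is left radical therapy, meaning surgery and radiotherapy.
- **SAP, Biopsy results.** Positive biopsy, under four definitions, is reported as cumulative frequency "with radical therapy as a competing risk". The analysis is repeated with radical treatment counted as an event.
- **Protocol 10.2.2.5.** "Eligible subjects who undergo additional radical therapy (surgery or radiation) after the VTP procedure or receive medical therapies (hormone or chemotherapies") stay in the intention-to-treat population but leave the per-protocol population.
- **Protocol synopsis, secondary endpoints.** "Use of secondary prostate cancer treatment following VTP will include surgical removal of the prostate gland, radiation treatment to the prostate gland", followed by hormones and chemotherapy.
- **Protocol 10.4.1.** The same endpoint appears with an open list of examples: "Patients who proceed to additional therapies for prostate cancer treatment such as radiation, surgery, hormone or chemo therapies will be documented".
- **Protocol 3.3, objective 9.** No limit by modality: "To document the occurrence of secondary prostate cancer therapies following VTP treatment".
- **Protocol synopsis, study design.** "Partial gland ablation therapy using thermal approaches, as an alternative to radical treatments for low-volume prostate cancer, is a treatment option currently being offered" in the U.S.

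**The concern.** The SAP separates ablation from radical therapy in one section, then uses only the narrower category where it decides how intervening treatment affects the biopsy results. Focused ultrasound or cryotherapy destroys prostate tissue, so a clean biopsy afterwards does not show that VTP worked. If ablation is neither a competing event nor an event, such a man stays in the biopsy curves as though VTP were his only treatment. The results at stake are the descriptive durability figures at months 24 to 60. Any bias in the repeat analysis favours VTP.

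**Working it through.** The plan states no figure on this point, so there is nothing to reproduce. The check compares the passages and adds one line of arithmetic.

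**Step 1: which rule recognises ablation?**

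| Rule | Surgery, radiotherapy | Ablation (focused ultrasound, cryotherapy) |
|---|---|---|
| SAP, time to additional therapy | event | event |
| SAP, biopsy results, main analysis | competing risk | not recognised |
| SAP, biopsy results, repeat analysis | event | not recognised |
| Protocol 10.2.2.5, per-protocol exclusion | excluded | not listed |

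The second column reads radical therapy as the SAP itself explains it in the additional-therapy section.

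**Step 2: who is exposed?** The secondary response endpoints cover biopsies on or before each month, and the SAP reports cumulative frequency. A qualifying positive biopsy before ablation is therefore already an event, and a later negative one does not remove it. The written exception is re-treatment after a positive month-3 biopsy, and in the protocol that re-treatment is VTP. The SAP's four definitions of positive are: (1) grade 4 or 5 anywhere, (2) any cancer anywhere, (3) grade 4 or 5 in the treated lobe, (4) any cancer in the treated lobe.

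| Biopsy finding before ablation | Already an event under | Still event-free under |
|---|---|---|
| Grade 4 or 5, treated lobe | 1, 2, 3, 4 | none |
| Grade 4 or 5, other lobe only | 1, 2 | 3, 4 |
| 3+3 only, treated lobe | 2, 4 | 1, 3 |
| 3+3 only, other lobe | 2 | 1, 3, 4 |
| No positive biopsy | none | 1, 2, 3, 4 |

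The gap concerns the last column only.

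**Step 3: size per man.** Let N be the men analysed, k those with a qualifying positive biopsy, r those with radical therapy and no qualifying positive biopsy, and a those with ablation, no radical therapy and no qualifying positive biopsy before or after. Assume no censoring.

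- Main analysis: k/N as written, and k/N if ablation becomes a competing event. The difference is 0.
- Repeat analysis: (k + r)/N as written, and (k + r + a)/N if ablation counts as an event. The difference is a/N.
- For a = 1 and N = 50 (planned enrolment): 1/50 = 2.0 percentage points.
- For a = 1 and N = 44 (minimum evaluable): 1/44 = 2.3 percentage points.

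If an ablated man later has a positive biopsy, the main analysis as written counts him. With ablation as a competing event it would not, which lowers the curve by 1/N. The favourable bias therefore lies in the repeat analysis. In the main analysis the change is mainly one of correct attribution.

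**The case against.** The strongest opposing case is that the documents already handle ablation where it matters, and most of it stands.

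- A reader might infer that the protocol and SAP contradict each other, so that a man given ablation is untreated in one and an event in the other and objective 9 has two answers. The documents do not support this. Section 10.4.1 gives examples rather than a closed list, objective 9 is unrestricted, and the synopsis wording is not clearly exhaustive. The protocol has no competing estimator: it describes these treatments and leaves detail to the SAP. The only time-to-treatment analysis already counts ablation, so no planned estimate of freedom from further treatment is overstated for this reason.
- A reader might also infer that ablation data will not be collected. The case report form is not among the documents, so this cannot be shown.
- The list in 10.2.2.5 does not decide who enters the SAP's biopsy analyses. Those use the SAP's efficacy population, whose definition has no explicit exclusion for later treatment. The list affects only the protocol's per-protocol descriptive results.
- The synopsis describes thermal ablation as an alternative to radical treatment, not as salvage after VTP, and section 6.4.11 names radical therapy as the follow-on option. Salvage ablation may be rare. However, the SAP plans a sensitivity analysis that removes ablative therapies, so its authors foresaw some.
- Cumulative endpoints narrow the exposure, as the second table shows.

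None of this answers the Biopsy results section, where both analyses leave ablation out.

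**Conclusion.** The point holds as an inconsistency within the SAP, with a matching gap in the protocol's per-protocol rule. A man ablated before he meets a given positive-biopsy definition remains event-free, and later negative biopsies are attributed to VTP in both biopsy analyses. Each such man makes the repeat analysis about 2 percentage points too favourable with 50 men analysed, assuming complete follow-up and no later positive biopsy. The main competing-risk curve barely moves. The number of such men is not given and is probably small.

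A reader might extend this to the primary result, because the SAP's rule on early pattern 4 or 5 disease also names only radical therapy. The documents do not settle that. Whether a man ablated before month 12 would be in the efficacy population depends on protocol compliance and on the investigator's judgement of major deviations. The point is limited to the secondary biopsy analyses.

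**What to change.** 1. In the SAP's Biopsy results section, replace radical therapy with additional prostate cancer treatment as the SAP defines it, both as the competing event and, above all, as the event in the repeat analysis. This also brings in hormonal therapy and chemotherapy, which the radical-therapy wording leaves out.
2. Keep a radical-therapy-only version of the biopsy analyses as a sensitivity analysis.
3. Add a derived variable for time to any additional treatment beside the existing one for time to radical therapy.
4. Align protocol 10.2.2.5 with the same definition. Citing it in the synopsis and in 10.4.1 is a wording change only.

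The cost is a few lines of text and one further set of biopsy results. The long-term figures may be slightly less favourable. The change affects analysis definitions only and does not bear on which further treatment a patient receives.

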2 BACKGROUND INFORMATION

2.1 Prostate Cancer: risk stratification and Treatment

Prostate cancer is one of the most common cancers in American men and a leading cause of cancer related suffering and mortality.¹ The incidence in 2012 was estimated at 413,000 new cases in the Americas and over 85,000 deaths. In the European Union, prostate cancer is the most commonly diagnosed cancer in men, and the third cause of cancer-related death.² In 2009, prostate cancer was the second most common cause of cancer-related death in US males and the leading type of cancer in men, with one-third of new cancer cases.³

Tumor stage and Gleason grade, used as the main predictors of risk in prostate cancer, have demonstrated a trend over time toward lower risk disease in US men. Among patients diagnosed with this disease, 46% are reported as being at low risk, 30% at intermediate risk, and 24% at high risk according to the D'Amico classification.^{4,5} The widespread adoption of PSA screening in clinical practice has led to an increased proportion of disease being diagnosed earlier when tumors are smaller and at lower stage^{4,6}, resulting in a very high rate of treatment among younger men and additional societal burden^{7,8}. Despite technological refinements in surgery and radiation therapy, radical whole-gland therapies cause erectile dysfunction in 30-70%, incontinence (requiring pad usage) in 5-10%, and rectal symptoms (diarrhea, bleeding, proctitis) in 5-20% of treated patients.⁹ New forms of conservative management designed to avoid treatment related toxicities have been developed to adapt to this shift toward smaller volume cancers identified at an earlier stage and are now being used in the U.S. and elsewhere, as an alternative to whole gland therapies.^{10,11,12,13,14,15}

These therapies which involve partial gland soft tissue ablation, also called focal therapy, are designed to appropriately address low volume prostate cancer at the proper scale to control the disease while maintaining normal organ function and have become standard therapies at U.S. centers.

Vascular-Targeted Photodynamic (VTP) therapy uses light delivered through optical fibers inserted in the tissue to activate circulating TOOKAD® Soluble (WST11; padeliporfin di-potassium) after its intravenous (IV) administration, in order to produce instantaneous vessel occlusion and subsequent tissue necrosis.^{16,17,18,19} By confining fiber placement to the prostatic tissue that contains the target tumors TOOKAD® Soluble-VTP offers the means to treat patients with early prostate cancer through partial gland ablation in a minimally invasive manner. TOOKAD® Soluble-VTP has a particular appeal in oncology because it does not preclude the use of other treatment modalities. Finally, TOOKAD® Soluble-VTP of the prostate is applicable in an ambulatory care setting and may be used as a repeatable procedure.

Localized treatment using TOOKAD® Soluble may offer an effective alternative to radical therapy in appropriately selected patients. This non-thermal form of partial gland ablation (PGA) is confined to the cancer containing prostate tissue while preserving adjacent normal tissue and, as a consequence, maintain organ functions. In localized, low-risk prostate cancer, hemiablation of the gland with TOOKAD®

Soluble VTP has been shown, in prospective clinical trials, to be an effective form of treatment with minimal side effects and negligible collateral damage to surrounding tissues. These results are in contrast to other forms of prostate hemiablation (e.g. cryotherapy and high intensity focused ultrasound (Hi-Fu)), which are thermal and have shown detrimental injury to surrounding tissues and greater impact on quality of life outcomes.^{20,21,22} TOOKAD® Soluble VTP is a novel type of treatment particularly addressed to patients who have early-stage disease (namely low and intermediate-risk patients). Patients successfully managed with this approach may then be spared the noxious secondary effect of radical treatments. This treatment, therefore, is designed to optimize quality of life outcomes while providing a means of controlling cancer progression in early stage patients that offers a management approach commensurate to the extent of their cancer.

2.2 TOOKAD® Soluble VASCULAR-TARGETED PHOTODYNAMIC THERAPY (VTP)

2.2.1 Historical Development

With a discovery program beginning in 2000, STEBA BIOTECH has developed a novel approach that relies on the bacteriochlorophyll derivatives, a novel generation of photosensitizers with unique attributes. The first compound of this family developed in prostate cancer was WST09. Several studies in patients with recurrent or previously untreated prostate cancer showed very promising results. WST11 (TOOKAD® Soluble) is a hydrophilic compound that is soluble in aqueous solutions and may be considered as the first in a class of focal vascular occluding agents.

